A fundamental component of the regenerative endodontic process is the presence of a scaffold for stem cells from the apical papilla to adhere, multiply and differentiate. Based on the results of many studies, the use of blood clot Regenerative procedure is not considered a true scaffold system. But it is an essential part of any appropriately designed tissue engineering regenerative endodontic strategy ⁽¹⁰⁻¹²⁾.

Different treatment options and scaffolds have been tested in regenerative endodontics. Only some of which exhibited clinical relevance such as blood clot, platelet rich plasma and platelet rich fibrin as RET scaffolds. Therefore, the use of suitable scaffold is an essential part of tissue engineering regenerative endodontic strategy ⁽¹³⁻¹⁶⁾.

Hence, developing a new dental material that retains the proteins or factors that can stimulate regenerative processes close to the natural process seems promising ⁽¹⁷⁾. Tissue-derived extracellular matrices have recently been known as naturally-derived scaffolds for tissue regeneration in various applications and have been revealed to serve as a cultural substrate on which cells tend to adhere to and proliferate well and can induce regeneration specific to tissues and sites ^(18,19)

A new extracellular matrix material, demineralized dentin matrix (DDM) derived from extracted teeth has been found to act as a biocompatible scaffold for the attachment, differentiation, and proliferation of human DPSCs (dental pulp stem cell) into odontoblast-like cells ⁽²⁰⁾. Dentine matrix has proposed roles for directing mineralised tissue repair in dentine and bone; however, the range of bioactive components in dentine and specific biological effects on bone-derived mesenchymal stem cells (MSCs) in humans are less well understood ⁽²¹⁾.

DDM is autogenous tooth dentin that has osteoconductive and osteoinductive potential since it contains extracellular collagen-1 and various growth factors. DDM as a solid blocky material has less physical stability and sealing ability as a material for regenerative endodontics. Therefore it has been further fabricated into their forms of DDM powder, gel, and as sheets in order to maintain bioactivity ⁽²²⁾.

DDM can be prepared with low risks of infection and rejection with noninvasive attainability; thus, it should be considered as a natural resource to be used to full advantage for other applications ⁽²³⁾.

In 2022 a meta-analysis performed by (**Grawish et al., 2022**)⁽²³⁾ indicated that DDM as a regenerative biomaterial has potential roles in tissue regeneration. However, in order to confirm these trials, further well-designed analyses are needed, and evaluation of adverse events in observational studies is also needed.

To our knowledge, DDM has not been investigated as scaffold in regenerative endodontics for permanent teeth.

Several studies were evaluate the regenerative effect of DDM at dentin-pulp complex through direct pulp capping technique, and it was found to possess the ability to activate the odontogenic differentiation of stem cells resident in the pulp tissues and induce reparative dentin formation. DDM also considered for alveolar ridge, maxillary sinus floor augmentations, socket preservation, furcation perforation repair, guided bone, and bioroot regenerations as well as bone and cartilage healing ⁽²³⁻²⁷⁾.

Hence, this study will be designed to evaluate regenerative effect of Demineralized Dentin Matrix as a scaffold in comparison to conventional blood clot in immature permanent teeth.

II. The null hypothesis

The null hypothesis is that there are no significance differences in the clinical and radiographic outcomes of regenerative endodontic of non-vital immature permanent teeth following the use of DDM in comparison to a blood clot scaffold.

III. Aim of the study

This study aims to:

Compare the clinical and radiographic outcomes of demineralized dentin matrix scaffold to blood clot scaffold in immature permanent incisors with non-vital pulps for one year.

IV. PICOTS

P: Patients ranging age 7–13years

I: Demineralized Dentin Matrix as a scaffold in Regenerative endodontic procedure

C: Blood clot scaffold Regenerative endodontic procedure

O: Clinical and radiographic success.

T: One year

S: outpatient's clinic of the Pediatric Dentistry and Dental Public Health Department, Faculty of Dentistry, Ain Shams University.

V. Methodology:

i. Study design

A Randomized, Controlled trial with 1:1 allocation ratio

ii. Sample size estimation

A power analysis was designed to have adequate power to apply a two-sided statistical test of the null hypothesis that there is no difference would be found between different groups. By adopting an alpha level of (0.05) a beta of (0.2) i.e. power=80% and an effect size (d) of

(1.51) calculated based on the results of a previous study ⁽²⁵⁾. the predicted sample size (n) was a total of (24) cases (i.e. 12 cases per group). Sample size was increased by 20% to compensate for possible dropouts during follow-up intervals to be (30) cases (i.e. 10 cases per group). Sample size calculation was performed using G*Power version 3.1.9.7⁽²⁸⁾

iii. Assignment of intervention:

a. Randomization and Allocation concealment.

1- Type: block Randomization, with blocks numbers of 10 and 1:1:1 allocation ratio in to 3 groups

Group I: DDM (study)

Group II: (control) blood clot

Group III: (+ control) blood clot with collagen

2- Sequence generation: the most senior supervisor will generate the sequence of random numbers using online randomization (www.random.org).

Allocation concealment and implementation:

Allocation concealment will be ensured by preparing opaque envelopes containing one number from the generated random sequence for assigned group. The most senior supervisor will select an envelope and reveal the treatment group at the final regeneration visit.

b. Blinding:

double blind study, participants, outcome assessors, statistician will be blinded.

iv. Study setting

This study will be conducted at the Outpatients Clinic at the Department of Pediatric Dentistry and Dental Public Health, Faculty of Dentistry, Ain Shams University.

ii. Study methodology

ethical regulation:

The study protocol will be submitted to the Research ethics committee, Faculty of Dentistry, Ain Shams University for approval.

V. Population

All parent or legal guardian fulfill the eligible criteria will be signed an informed consent before beginning any procedure, explaining detailed treatment procedures, the possible outcomes, comprehensive discussions of the risks, complications, alternative treatment options, follow-up period needed, and sequel of no treatment⁽⁸⁻¹⁴⁾.

Inclusion criteria:

- (1) Age 7–13 years at the time of enrolment.
- (2) Provision of informed consent by one parent or legal guardian.
- (3) At least one immature permanent anterior tooth diagnosed with irreversible pulpitis or pulp necrosis with or without periapical lesions.
- (4) Restorable teeth.
- (5) Compliant patient/parent.
- (6) Patients not allergic to medicaments and antibiotics necessary to complete procedure (ASA 1 or 2).
- (7) Radiologic evidence of open apices (Teeth are considered immature when a minimum of 1 mm apical foramen width is evident)

Exclusion criteria

- (1) Teeth with root fractures or split roots.
- (2) Presence of root resorptions.
- (3) Presence of periodontal pockets.
- (4) Developmental anomalies
- (5) Presence of periapical radiolucency more than 10 mm
- (6) Tooth with class III mobility.

vi. Clinical Procedures

a. Screening Recruitment

Patients attending the outpatient's clinic of the Pediatric Dentistry and Dental Public Health Department, Ain Shams University will be screened for eligibility. Only patients who met the inclusion criteria and sign the informed consent will be conveniently enrolled in the study until

the predetermined sample size is reached. All examination procedures will be done by the same operator to ensure standardization.

b. Informed Consent

A signed informed consent from parent or legal guardian, and an oral assent to the child, as outlined by the Research Ethics Committee, Faculty of Dentistry, Ain Shams University will be obtained before the conduction of the study.

Grouping:

Eligible immature anterior teeth will be randomly allocated in two groups:

Group I: 10 teeth will be treated with demineralized dentin matrix as scaffold in regenerative endodontic procedure.

Group II: 10 teeth will be treated with conventional regenerative endodontic procedure (blood clot scaffold).

Group III: 10 teeth will be treated with regenerative endodontic procedure (bloodclot and collagen scaffold).

Clinical procedures:

Pre-operative periapical radiograph and cone beam computed tomography CBCT will be taken on the selected non-vital tooth in each child before the beginning of the regenerative endodontic treatment procedure (29, 30).

RET will be carried out according to ASE⁽⁸⁾

First Appointment

- Local analgesia will be delivered (2% lidocaine with 1:100,000 adrenaline).
- Following rubber dam isolation and access cavity preparation, pulp tissue extirpation/debridement
- The root canal system will be minimally instrumented.
- Copious irrigation will be performed, gently with 20ml NaOCl (1.5% NaOCl (20mL/canal, 5 min) using 0.3mm gauge single side vented needles, adjusted 3 mm short of the apex.
- then canal will be irrigated with EDTA (20 mL/canal, 5 min), with irrigating needle that will be positioned about 1 mm shorter than the root end, to minimize cytotoxicity to stem cells in the apical tissues, followed by a final rinse 20 mL sterile saline .

- Canals will be dried with paper points.

double antibiotic paste, ciprofloxacin (Ciprocin 250mg tablets) and Metronidazole (Flagyl 500mg tablets) in a 1:1 ratio will be mixed with sterile distilled water in a 3:1 ratio, then will be introduced into the root canal systems using 18 G hypodermic needle and will be packed gently down the root canal using a hand plunger, ensuring that there will be no remains coronal to CEJ

- A sterile dry cotton pellet will be placed over the paste after which the tooth will be sealed with 3-4mm of a temporary restorative material.
- Patient will be dismissed for 2 week

Second Appointment (two week after 1st visit)

- Response to initial treatment will be assessed. If there are signs/symptoms of persistent infection, additional treatment time with antimicrobial.
- Local Anesthesia without vasoconstrictor will be administered; dental dam isolation will be achieved.
- Copious gentle irrigation will be performed with 20ml of 17% EDTA, followed by a final rinse 20 mL sterile saline.
- Canals will be dried with paper points.

In group I: teeth will be treated with demineralized dentin matrix as scaffold in regenerative endodontic procedure

Teeth, in this group, will be anaesthetised using a local anaesthetic without vasoconstrictor. Demineralized dentin matrix will be introduced inside the root canal and bleeding will be created into root canal by over-instrumentation by rotating K-file at 2 mm past the apical foramen with the goal of having the entire canal filled with blood to the level of the cemento-enamel junction.

A lightly moistened sterile cotton pellet will be placed into the canal, 3-4 mm apical to the CEJ, for 7-10 minutes to allow blood clot formation.

Placement of the bioactive and restorative materials: A bioactive material such as tricalcium silicate will be placed over the blood clot as a capping material. A 3-4 mm layer of glass ionomer will be gently placed over the capping material.

Followed by resin composite restoration ⁽¹⁶⁾.

In group II: teeth will be treated with conventional regenerative endodontic procedure (blood clot scaffold).

Teeth, in this group, will be anaesthetised using a local anaesthetic without vasoconstrictor. Bleeding will be created into root canal by over-instrumentation

A lightly moistened sterile cotton pellet will be placed into the canal, 3-4 mm apical to the CEJ, for 7-10 minutes to allow blood clot formation.

Placement of the bioactive and restorative materials as mentioned above.

In group III: teeth will be treated with conventional regenerative endodontic procedure (blood clot and collagen scaffold).

Teeth, in this group, will be anaesthetised using a local anaesthetic without vasoconstrictor. Bleeding will be created into root canal by over-instrumentation

A collagen will be placed into the canal, apical to the CEJ.

Placement of the bioactive and restorative materials as mentioned above

e. Follow up

Clinical and Radiographic examination will be carried out during follow up period^(15, 16).

1- Clinical evaluation: Treatment success will be assessed using following criteria of success.

Criteria of success: Absence of

- Pain
- Soft tissue swelling
- Soft tissue inflammation
- Sinus tract
- tenderness to percussion
- tooth mobility

2- Radiographic evaluation:

A-Conventional radiographic evaluation:

Criteria of success:

- Apical foramen width reduction
- Increased dentinal wall thickness
- Increased root length
- Conventional radiograph showing progress bone healing and presence of a normal periodontal ligament space.
- Reduction in size of the lesion.

B- CBCT evaluation:

- CBC with limited field of view will be carried out at 12 month to asses dentin width and length^(23, 28)

f. Outcome measurement

Outcome	assessment	Assessment method
Primary outcome	1- pain 2-pain percussion 3-pathological mobility 4- gingival becket	1-visual assessment 2-percussion test 3-blunt ends of two examination mirrors 4-graduated metal periodontal probe
Secondary out com	1-Root length 2-Root dentinal thickness 3- Apical foramen width 4- Total radiographic root area (absence of internal and external root resorption, widening of periodontal ligament space, new preabical radiolucencies or enlargement of pre-existing lesion, pulp canal calcification)	Digital periapical radiograph examination with using paralleling device
Secondary outcome	Increased root wall thickness and increased root length.	CBCT with limited field of view

VII. Statistical analysis

Categorical data will be represented as frequency (n) and percentage (%) and will be analyzed using chi square test. Numerical data will be explored for normality by checking the data distribution, calculating the mean and median values and using Kolmogorov-Smirnov and Shapiro-Wilk tests. If the data was found to be normally distributed, it will be presented as mean and standard deviation values and paired t-test will be used for the analysis. If the assumption of normality was found to be violated; the data will be presented as median and range values and will be analyzed using Signed rank test. The significance level will be set at $p \leq 0.05$ for all tests. Statistical analysis will be performed with IBM SPSS Statistics Version 26 for Windows.

VIII. Study timeline

This study will be conducted from October 2023 to October 2024.

X. Patient withdrawal

- Patients who aren't willing to continue in the study will have the right to quit at any time without loss of any benefits.
- Patients who don't comply with the oral hygiene measures given will be excluded from the study and will be offered to continue dental treatment at the departments' outpatient clinic.
- Any adverse event will be recorded and managed promptly. In addition, in failure occurs, the use of the experimental material will be stopped and patients will be treated with another modality.

[figure not shown]
xi. Data management

Patient information will be guarded as confidential information that should never be revealed at all times.

All information will be kept as a hard and soft copy.

xii. Adverse event reporting

Regenerative treatment is not expected to have any adverse side effects on health but if failure occurs in the regenerative treatment, conventional regenerative endodontic treatment will be fabricated.

xiii. Ethics and dissemination

a. Research ethics approval:

This protocol and the template informed consent form contained in Appendix are written following the guidelines outlined by the Research Ethics Committee and Institutional Review Board, Faculty of Dentistry, Ain Shams University.

b. Protocol amendments:

In case of protocol modifications, the Research Ethics Committee and Institutional Review Board, Faculty of Dentistry, Ain Shams University will review and approve the changes of protocol before proceeding and implementation of changes.

c. Informed consent:

A verbal as well as a written consent will be obtained from the caregivers of the participants after explaining the objectives of the study and assuring complete confidentiality of data. All caregivers and participants will be informed that they have the right to withdraw from the study at any time. Moreover, participants 6 years and older will be requested to sign an assent form after an age appropriate explanation of the trial procedures and their objectives. All consent and assent forms are translated into Arabic (APPENDIX I).

d. Confidentiality

All study-related information will be stored securely at the study site. Personal information, consent forms of enrolled participants will be collected by the primary investigator (candidate) and stored in hard copy examination sheets in locked file cabinets with limited access. All local databases will be secured on password-protected computers. Patients' identity will not be shared at any stage of the study. Participants receiving treatment will be given codes (identification numbers) for statistical analysis.

e. Access to data:

Primary investigator, supervisors and biostatistician will have access to the final trial dataset.

f. Post-trial care

All patients with premature loss of teeth in the patients' mouth will be treated with the proper treatment protocol. According to our knowledge, no side effects have been reported in literature from using both materials under study in patients with non-vital immature permanent teeth.

g. Dissemination policy

After completion of the study, trial results will be communicated to participants – if interested – via phone calls. Results, as well as some radiographs and clinical pictures of treated teeth, will be available for healthcare professionals and the public via publications.

Guidelines for authorship will follow the four criteria stated by the International Committee of Medical Journal Editors -ICMJE|. Contributors meeting less than the four criteria will be acknowledged.

h. Declaration of interest

The investigators declare no conflict of interest.

References

1. Cummins D. (2013): Dental caries: a disease which remains a public health concern in the 21st century--the exploration of a breakthrough technology for caries prevention. *J Clin Dent.*, 24 Spec no A: A1-14.

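### The 80% power belongs to d = 1.51 on an unnamed variable with 8 teeth per group, not the stated 12, and does not cover the clinical primary outcome

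*Protocol*

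**What the plan says.** **Sample size (Protocol, V.ii).** The paragraph specifies a two-sided test: "By adopting an alpha level of (0.05) a beta of (0.2) i.e. power=80% and an effect size (d) of" 1.51, where the value is described as "1.51) calculated based on the results of a previous study". No variable, mean difference or standard deviation is given. The result is stated as "the predicted sample size (n) was a total of (24) cases (i.e. 12 cases per group"), and then "Sample size was increased by 20% to compensate for possible dropouts during follow-up intervals to be (30) cases (i.e. 10 cases per group").

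**Number of groups.** The study design section gives 1:1 allocation. The randomisation section gives "1:1:1 allocation ratio in to 3 groups". The Grouping section announces two groups and then lists three, with 10 teeth each.

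**Outcome.** The null hypothesis (section II) is of "no significance differences in the clinical and radiographic outcomes" between DDM and blood clot. PICOTS (section IV) gives "O: Clinical and radiographic success". The primary row of section f (Outcome measurement) lists "1- pain 2-pain percussion 3-pathological mobility 4- gingival becket" with an examination method for each and no scale. Section e (Follow up) defines clinical success as the absence of six signs: pain, swelling, soft-tissue inflammation, sinus tract, tenderness to percussion and mobility. Section VII assigns categorical data to the chi-square test.

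**The concern.** There are three linked problems.

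- **The per-group figure.** An increase for dropout cannot turn 12 per group into 10, so at least one of the two figures is wrong.
- **The endpoint behind the power.** d is a difference in means divided by a standard deviation. It says nothing about power to compare success proportions. The paragraph names no endpoint and the only null hypothesis covers clinical and radiographic outcomes, so a reader will take the 80% as covering the primary. A non-significant result could then be read as equal success when the trial had little chance of showing a difference.
- **Two lists for clinical success.** Swelling, soft-tissue inflammation and sinus tract appear only in section e. The pocket item appears only in the primary row. A tooth with a sinus tract and none of the four primary signs passes one list and fails the other. With 10 teeth per arm, one reclassified tooth moves that arm's rate by 10 percentage points.

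**Working it through.** **1. The plan's own figure.** Inputs from section V.ii: d = 1.51, two-sided alpha 0.05, power 80%. For a two-sample t-test with n per group, the noncentrality is d × √(n/2) on 2n − 2 degrees of freedom. Power is the probability that this noncentral t exceeds the critical value in either direction.

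| n per group | noncentrality | critical t | power |
|---|---|---|---|
| 7 | 2.825 | 2.179 | 73.7% |
| 8 | 3.020 | 2.145 | 80.2% |
| 10 | 3.376 | 2.101 | 89.1% |
| 12 | 3.699 | 2.074 | 94.2% |

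The inputs therefore need 8 per group. With 12 per group, 80% power corresponds to d = 1.20, not 1.51.

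**2. The totals.**
- Three groups of 8: 3 × 8 = 24, and 24 / 0.8 = 30 = 3 × 10. This matches both totals and the final 10 per group.
- Two groups of 12: 2 × 12 = 24, and 24 / 0.8 = 30 = 2 × 15. This matches the totals but not the final 10 per group, and not d = 1.51.
- Three groups of 12: 3 × 12 = 36, and 36 / 0.8 = 45. This matches neither total.

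Only 8 per group fits d, both totals and the final allocation together. The 12 looks like 24 divided by two groups.

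**3. Power for a success/failure primary, pairwise (DDM versus blood clot).** The protocol gives no success rates, so the differences below are assumptions. Power is the sum of the two binomial probabilities over all tables with p ≤ 0.05. Each entry is the maximum over every possible baseline rate, so it is the most favourable case for the plan.

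| Teeth per arm | Difference | Chi-square, uncorrected | Fisher |
|---|---|---|---|
| 10 | 10 points | 6.3% | 2.2% |
| 10 | 15 points | 9.0% | 3.6% |
| 8 | 10 points | 10.0% | 3.2% |
| 8 | 15 points | 13.0% | 4.5% |

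The chi-square figures are higher at 8 than at 10 per arm partly because that test's type I error reaches 7.7% at 8 per arm, against 4.2% at 10.

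**4. Three-group chi-square (2 degrees of freedom).** Section VII does not say whether the test is pairwise or across all groups. If the collagen arm lies anywhere between the other two, the maximum power at 10 per arm is 9.0% for 10 points and 18.0% for 15 points. At 8 per arm it is 7.7% and 11.4%.

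**5. What 10 per arm can detect.** Against an assumed 95% success rate, pairwise power is:
- 95% versus 40%: chi-square 79.6%, Fisher 63.3%
- 95% versus 30%: chi-square 91.3%, Fisher 80.5%

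**6. Size needed for 80% power on a binary primary.** The usual formula with pooled variance under the null gives 76 teeth per arm for an assumed 95% versus 80%, and 141 for 95% versus 85%.

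**The case against.** The strongest reply is that the trial is not undersized for its own d. Ten per group leaves 8 after 20% loss, which is what one pairwise t-test at d = 1.51 needs. On that reading the totals are right and the numerical slip is a single per-group figure. This stands, and it is why the number of teeth need not change.

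The binary reading is also an inference. The primary row gives no scale and does not call itself clinical success. Pocket depth could be recorded in millimetres and mobility could be graded. That is fair, but PICOTS, the success criteria in section e and the chi-square rule all point to success or failure, and nothing in the protocol links d = 1.51 to a numeric pocket depth or a mobility grade. The 80% is unsupported for the primary on either reading.

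The 10- and 15-point differences are the review's choice, and the three-group maxima assume that the collagen arm lies between the other two. Both are assumptions. The pairwise figures do not need the second, and they take the best case over baseline rates.

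The four-item and six-item lists are a separate defect from the arithmetic. They belong here only because any honest power statement for the primary needs a single definition of it.

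**Conclusion.** The concern holds. The stated 80% does not match the stated 12 per group (94.2% at d = 1.51; 8 per group gives 80.2%), and 12 per group cannot be raised to 10. No variable is attached to d, so the power statement cannot be carried to the clinical primary outcome.

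If that outcome is analysed as success or failure, power across all the readings above is at most 10% for a 10-point difference and 18% for a 15-point difference. With 10 per arm, roughly 80% pairwise power needs something like 95% versus 40% by chi-square, or 95% versus 30% by Fisher. The t-test result rests only on the protocol's inputs. The binary results rest on assumed differences and rates, on the success/failure reading and, for the three-group test, on an intermediate collagen arm.

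This must be fixed, because the paragraph is wrong as written and invites a misreading of a null result.

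**What to change.** Keep the 30 teeth and amend two places.

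1. **Section V.ii.** Ask the sponsor to name the variable, mean difference and standard deviation behind d = 1.51 from the G*Power record. Change the per-group figure to 8 evaluable, 10 after the dropout allowance. If the record shows that 12 was meant, say that 30 teeth in three groups cannot supply it. State that 80% power applies only to a pairwise difference in means of d = 1.51 on that variable; if it cannot be identified, say so. Add that the trial is not powered for its clinical primary, giving the detectable pairwise difference at 10 per arm with its assumption: about 95% versus 40% (uncorrected chi-square) or 95% versus 30% (Fisher), with the 95% assumed.

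2. **Sections e and f.** Reconcile the four-item and six-item lists into one definition of clinical success; a single binary composite is one option. Report the DDM versus blood clot risk difference with an exact 95% confidence interval, and do not read non-significance as equal success. If outcome data have already been seen, label the definition as post hoc.

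**Cost.** One amendment through the ethics committee, no extra patients or examinations, and a less favourable power statement. The change does not raise power; that would need the arm sizes in step 6 of the working.

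### The sample-size text gives 12 cases per group before a 20% increase and 10 per group after it, and the protocol describes both a two-group 1:1 and a three-group 1:1:1 trial; 12 per group is the figure that does not fit.

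*Protocol*

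**What the plan says.** Protocol, section V.ii (Sample size estimation), sets a two-sided test, alpha 0.05, beta 0.2 (80% power) and an effect size d of 1.51 from an earlier study, calculated in G*Power. It reports that "the predicted sample size (n) was a total of (24) cases (i.e. 12 cases per group". The next sentence adds 20% for dropout and arrives at a sample size "to be (30) cases (i.e. 10 cases per group".

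The number of arms is given in three places:

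- Section V.i (Study design): "A Randomized, Controlled trial with 1:1 allocation ratio". The null hypothesis, the aim and the PICOTS list likewise name only demineralized dentin matrix (DDM) and blood clot.
- Section iii.a (Randomization and Allocation concealment): "block Randomization, with blocks numbers of 10 and 1:1:1 allocation ratio in to 3 groups".
- Grouping: "Eligible immature anterior teeth will be randomly allocated in two groups", followed by three groups of 10 teeth, the last being "Group III: 10 teeth will be treated with regenerative endodontic procedure (bloodclot and collagen scaffold".

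The Outcome measurement table lists as primary outcomes "1- pain 2-pain percussion 3-pathological mobility 4- gingival becket". Section VII (Statistical analysis) says: "Categorical data will be represented as frequency (n) and percentage (%) and will be analyzed using chi square test".

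**The concern.** The two sample-size sentences cannot both be right, since allowing for dropout raises the number per group and here it drops from 12 to 10. The first sentence implies two arms (24 = 2 × 12) and the second implies three (30 = 3 × 10). The same split between two and three arms runs through Study design, Randomization and Grouping.

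What is at stake is the required number of evaluable cases per group. If it is 8, enrolling 10 covers it and only the text is wrong. If it is 12, enrolling 10 per group misses it even with no dropout.

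The section also does not say what the 80% refers to. An effect size d with a two-sided test describes one two-group comparison of means, whereas the primary outcomes are clinical findings such as pain and mobility, and categorical data go to a chi-square test.

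**Working it through.** **Inputs** (Sample size estimation): d = 1.51, two-sided alpha 0.05, power 80%, dropout 20%. The section names no test. Because d is the effect size for two means, I take a two-sample t-test with n per group.

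**Step 1. Does 12 per group reproduce?** Power comes from the noncentral t distribution with df = 2n − 2, noncentrality δ = d·√(n/2) and critical value t(0.975, df):

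| n per group | δ = 1.51·√(n/2) | Critical t | Power |
|---|---|---|---|
| 7 | 2.825 | 2.179 | 73.7% |
| 8 | 3.020 | 2.145 | 80.2% |
| 10 | 3.376 | 2.101 | 89.1% |
| 12 | 3.699 | 2.074 | 94.2% |
| 15 | 4.135 | 2.048 | 97.9% |

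The smallest n reaching 80% is 8, not 12. Read the other way, the effect detectable with 80% power is d = 1.507 at 8 per group, 1.325 at 10 and 1.197 at 12. The stated 1.51 matches 8.

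**Step 2. Other single choices of method.** Required n per group at d = 1.51:

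| Variant | n per group |
|---|---|
| One-sided t-test | 7 |
| Mann-Whitney | 9 to 10 |
| Three-group ANOVA, depending on the pattern of means | 7 to 10 |
| Bonferroni for two comparisons | 10 |
| Bonferroni for three comparisons | 11 |
| 90% power | 11 |
| 95% power | 13 |
| Paired t-test | 6 pairs |

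None gives 12.

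**Step 3. Which number of arms fits the totals?**

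| Reading | Before dropout | After dropout | Agrees with 10 per group? |
|---|---|---|---|
| Three arms, 8 each | 3 × 8 = 24 | 8/0.8 = 10 per arm; 24/0.8 = 30 | Yes |
| Two arms, 12 each | 2 × 12 = 24 | 12/0.8 = 15 per arm; 2 × 15 = 30 | No |
| Two arms, 8 each | 2 × 8 = 16 | 16/0.8 = 20 | Per group yes, totals no |
| Three arms, 12 each | 3 × 12 = 36 | 36/0.8 = 45 | No |

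A literal 20% increase on the total gives 24 × 1.2 = 28.8, that is 29. The 30 comes from dividing by 0.8, or from 8 × 1.2 = 9.6 rounded up to 10 in each of three arms. The totals 24 and 30 fit both of the first two rows. Only three arms of 8 also match the 10 per group, the three listed groups of 10 teeth and d = 1.51.

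**Step 4. What the 80% covers.** At 8 evaluable per group it holds for one unadjusted comparison. As an illustration only, since the protocol plans no adjustment, the same comparison at 0.05/3 has 62.4% power with 8 per group and 76.1% with 10.

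**Step 5. Blocks.** Ten blocks of three give 10 × 3 = 30, split 10:10:10. A block size of 10 cannot be split equally among three arms, because 10/3 is not a whole number.

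**The case against.** The strongest objection concerns certainty. The protocol names G*Power but no test, outcome or number of comparisons, so 8 per group rests on assuming an unadjusted two-sample t-test. On the totals alone, two arms of 12 rising to 15 work equally well, and the hypothesis, aim, PICOTS and 1:1 ratio all describe two arms; on that reading, 10 per group is the slip. Some combined methods do reach 12: Mann-Whitney at efficiency 0.955 with Bonferroni for three comparisons (83.4% at 12, 78.9% at 11), or at efficiency 0.864 with Bonferroni for two (83.2% at 12). The figure of 8 is also close to its limit: an unrounded d of 1.505 would give 79.9%.

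That stands as a reason to ask the sponsor to confirm 8. It does not rescue the text. The combined methods need adjustments the protocol does not state, and 12 in each of three arms would total 36, not 24. The two-arm reading conflicts with d = 1.51 and with the three listed groups.

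It is also fair to say that the trial as it will be run has three arms, because the clinical procedures describe all three groups; the two-group phrases look like uncorrected text. Ten blocks of three is a natural reading of the block wording, so that item only calls for clarification. Finally, if 8 is confirmed, the harm is confined to the text. The correction is still needed, because the text misstates the per-group requirement and the allocation, both of which define the design.

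**Conclusion.** The concern holds. The contradiction is printed in complete sentences and does not depend on any assumption: 12 per group before an increase and 10 after it, alongside a two-group 1:1 and a three-group 1:1:1 design.

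The likely resolution, conditional on a single unadjusted two-sample t-test, is 8 evaluable and 10 enrolled per group in three arms. The 12 then looks like a two-arm split of 24 left in the text. On that resolution the totals of 24 and 30 stand, and power for the one comparison is 80.2% after 20% dropout and 89.1% with none. If 12 evaluable per group is truly required, enrolment is at least 2 per group short before any loss, and 4 short after 20% dropout (12 − 8).

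On neither resolution do the stated inputs support an 80% claim for three pairwise comparisons or for the categorical primary outcomes.

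**What to change.** 1. In Sample size estimation, after confirming the original calculation, state for example: 8 evaluable cases per group (24 in total) give 80% power for a two-sided two-sample t-test at 0.05 with d = 1.51; allowing for 20% dropout, 10 per group (30 in total) will be enrolled. If the sponsor holds that 12 per group is required, say instead that 10 enrolled per group does not meet it.
2. Add that the 80% applies to one unadjusted comparison, DDM versus blood clot, on a named continuous outcome, and does not extend to all three pairwise comparisons or to the categorical primary outcomes. The sponsor must name the outcome from which d = 1.51 was taken, as the protocol does not identify it.
3. Write three groups and 1:1:1 in Study design and Grouping, to agree with Randomization.
4. Clarify the block wording. If ten blocks of three were meant, say so; if a block size of 10 was meant, replace it with a multiple of 3.

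Cost: protocol wording only, with no extra patients, if 8 per group and ten blocks of three are confirmed. The allocation list changes only if a block size of 10 was used.
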